9.3.3 Covariates

The following patient characteristics will be assessed in this study:

Demographic characteristics:

- Age on the index date (continuous variable in years)
- Age on the index date (categorical variable: 18-34 years, 35-49 years, 50-64 years, 65 years and above)
- Gender (male, female)
- Ethnicity (if available)
- Patient level Index of Multiple Deprivation (IMD)

Lifestyle factors

- Smoking status (closest to index date; if available)
- Alcohol consumption (closest to index date; if available)
- Body mass index (BMI) (closest to index date; if available)
- Systolic and Diastolic Blood pressure measurement (closest to index date; if available)

Asthma history and lab tests

- Number of asthma exacerbations in the year prior to the index date. This is defined as as ≤ 300 mg oral corticosteroids (OCS) (not prescribed during an annual asthma review), or an Accident and Emergency (A&E) visit, or hospital admission. Exacerbations recorded within 14 days after the index 1 were considered part of the same exacerbation.
- Royal College of Physicians (RCP) 3 Questions for Asthma score on the index date, or when it was not recorded on the index date, during the pre-index period (the one closest to the index date) (each question scored 0 (no) or 1 (yes) for the following three questions: “Have you had difficulty sleeping because of your asthma symptoms (including cough)?” “Have you had your usual asthma symptoms during the day (cough, wheeze, chest tightness or breathlessness)?” and “Has your asthma interfered with your usual activities (e.g., housework, work, school, etc)?” [R18-1720]).
- Number of all-cause hospitalization in the year prior to the index date
- Number of respiratory disease related hospitalization in the year prior to the index date

Protocol for non-interventional studies based on existing data

BI Study Number 0205-0537

c25002535-01

Proprietary confidential information © 2018 Boehringer Ingelheim International GmbH or one or more of its affiliated companies

- Eosinophil count on the index date, or when it was not recorded on the index date, during the pre-index period (the one closest to the index date) (if available)

Comorbidities

- Respiratory
 - Pneumonia
 - Bronchiectasis
- Cardiovascular
 - Ischaemic heart disease
 - Myocardial infarction (MI)
 - Angina pectoris
 - Aneurysm
 - Hypertension,
- Renal failure
- Diabetes mellitus (any type)
- Psychiatric disorders
 - Dementia
 - Delerium
 - Depression
- Stroke
- Allergic rhinitis
- Sinusitis
- Charlson comorbidity index [[R08-1584](#)]
- Cataract
- Osteoporosis
- Obesity

Concomitant prescriptions

- Asthma-related prescriptions in the year prior to index date
 - Short-acting beta agonists
 - Inhaled long-acting beta agonists (on top of ICS/LABA FDC)
 - Inhaled corticosteroid (ICS) (on top of ICS/LABA FDC)
 - Oral corticosteroid
 - Theophylline
 - Leukotriene Receptor Antagonist (LTRA)
 - Azithromycin,
 - Mucolytics
- Cardiovascular medications
 - Cardiac Glycosides
 - Thiazides
 - Loop diuretics
 - Antiarrhythmics
 - Beta blocker
 - Vasodilator Antihypertensive Drug
 - Centrally Acting Antihypertensive Drugs
 - Alpha-adrenoceptor Blocking Drugs
 - Drugs affecting the renin-angiotensin system

- Angiotensin Converting Enzyme Inhibitors
- Angiotensin II receptor blockers
- Renin Inhibitors
- Other antihypertensives
- Nitrates
- Calcium channel blockers
- Oral anticoagulants
- Heparin and other low molecular weight heparins
- Aspirin
- Antiplatelet
- Lipid-regulating Drugs
 - Bile Acid Sequestrants (lipid-regulating Drugs) - including Colesevelam
 - Ezetimibe (only in combination with Statin)
 - Fibrates
 - Statins
 - Nicotinic Acid Group
 - Omega-3 Fatty Acid Compounds
 - Other lipid-regulating drugs
- Glucose-lowering agents
- Non-steroidal anti-inflammatory drugs
- Psycholeptics
- Antipsychotics
- Antidepressants
- Agents for dementia

For concomitant medications used for diseases other than asthma the look-back time period will be limited to 180 days prior to the index date to increase the likelihood that the medications were used concomitantly. Concomitant medications will be categorized as current use (up to and including 60 days before index date) and past use (use any time prior to the 60 days before index date).

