9. RESEARCH METHODS

9.1 STUDY DESIGN

This study is a cross-sectional, non-interventional study based on existing data (NISed). The UK CPRD data will be used to assess the characteristics of asthma patients who were prescribed ICS/LABA FDC before the index date and who initiated Spiriva Respimat, or received a higher dose of ICS/LABA FDC, or initiated LTRA, or switched to a new ICS/LABA FDC in the UK during the study period (September 2014-December 2017). This will allow us to assess potential channeling of prescribing to different patient populations.

Note: Study period: September 2014-December 2017.

This is a cross-sectional study and patients will not be followed up after the index date.

Patient characteristics will be evaluated on the index date, or when a characteristic was not recorded on the index date, during the pre-index period (the one closest to the index date).

In the UK, nearly all residents are registered in a general medical practice that uses electronic medical records. Some of those records are available for research purposes in the CPRD. CPRD contains diagnostic and prescribing information recorded by general practitioners (GPs) as part of their routine clinical practice in the UK. The database currently contains data for over 13.2 million patients with research-quality data from 680 UK practices; 5.69 million of these patients are active (still registered with a contributing GP practice) [[R14-5257](#)]. Patients registered are representative of the whole UK population in terms of age and sex. More detailed description of the CPRD data is provided in [section 9.4](#).

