9.3 VARIABLES

All the variables will be identified based on data recorded on the index date (date of dispensing/initiation of the exposure), or when a characteristic was not recorded on the index date, during the pre-index period (the one closest to the index date), unless otherwise specified.

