9.7.3 Missing values

No imputation will be done for missing values. For all covariates, missing values will be presented as a separate category.

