9.9 LIMITATIONS OF THE RESEARCH METHODS

The main analysis will exclude patients with other respiratory disease (e.g., COPD). This will exclude asthma-COPD overlap patients and some other patients and the results may not be representative to all asthma patients. However, Spiriva has both asthma and COPD indications. Therefore, for asthma-COPD overlap patients, the reason for initiating Spiriva Respimat can be unclear in existing data. Since the primary objective is to describe the characteristics of asthma patients prior to the initiation of Spiriva Respimat for the treatment of Asthma, it would be reasonable to exclude asthma-COPD overlap patients,

This study is based on existing data. It is possible that misclassification may happen for the measurement of comorbidities. However, we will use all the available data before the index date to minimize the possibility of misclassification.

Some covariates such as smoking status, alcohol use, BMI, pulmonary function, and eosinophil count may not be well recorded in CPRD. In the analyses we will present missing data as a separate category.

Some information may be recorded very infrequently or not at all in CPRD, e.g., number of people in a household, over-the-counter medication use, prescriptions in secondary care. These variables will not be assessed in this study.

The CPRD only includes patient data captured from general practitioners. Although some information about patient contacts with secondary care could be manually entered into the patient record, details about these specialty visits and hospital admissions (including dates, diagnoses, tests performed, length of stay) may be incomplete.

The CPRD may not be representative of all practices in the UK based on geography and size. There are certain patient groups that are missing from primary care records, such as prisoners, private patients, some residential homes and the homeless. Thus, selection bias cannot be ruled out. However, studies suggested that CPRD patients are broadly representative of the UK population in terms of age and sex. Patients are also comparable to the UK census in

terms of ethnicity, and comparable to the Health Survey for England for body mass index distribution in most patient subgroups.

The HES APC data and HES A&E data only have data for patients from England.

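### Smoking status comes from the single record closest to index, so a latest 'never' entry stands even when earlier records show smoking

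*Protocol*

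**What the plan says.** Section 9.3.3 lists the variable among the lifestyle factors as "Smoking status (closest to index date; if available"). This repeats the general rule. Section 9.1 states "Patient characteristics will be evaluated on the index date, or when a characteristic was not recorded on the index date, during the pre-index period", and section 9.3 takes a value not recorded at index from a record "during the pre-index period (the one closest to the index date), unless otherwise specified". Nothing makes smoking an exception, and the smoking categories are not listed.

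Section 9.9 (limitations) concedes that "Some covariates such as smoking status, alcohol use, BMI, pulmonary function, and eosinophil count may not be well recorded in CPRD". The answer given there is "In the analyses we will present missing data as a separate category", and section 9.7.3 repeats it: "For all covariates, missing values will be presented as a separate category". Section 9.9 also promises that "we will use all the available data before the index date to minimize the possibility of misclassification", but the sentence before it limits the subject: "It is possible that misclassification may happen for the measurement of comorbidities".

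Under section 9.7.1, covariates are compared between Spiriva Respimat and each other group by ASD, and 10% or more counts as meaningful.

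**The concern.** For BMI, blood pressure or current smoking, the latest value is the right one to take, because each is a present state. 'Never smoker' is different: it is a statement about the whole past, and an earlier smoker or ex-smoker entry contradicts it. A rule that reads one record cannot see the contradiction, although the earlier records are in the same database.

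Smoking history matters here for three reasons that the protocol supplies. The aim is to assess channeling. The drug has both asthma and COPD indications (section 9.9), while COPD is excluded only by recorded code (section 9.2 and Annex 4). And section 7 says the results may guide the choice of propensity-score variables in later studies. Understated past smoking would blur a characteristic that readers will look at when they ask who is being prescribed the drug.

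**Working it through.** **1. What the rule does.** Take a patient with these entries and an index date in 2017:

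| Record | Entry |
|---|---|
| 2008 | current smoker |
| 2012 | ex-smoker |
| 2016 | never smoked |

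Under section 9.3.3 the 2016 entry is used and the patient is tabulated as never. Remove the 2016 entry and the same patient is an ex-smoker.

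**2. Whether another passage prevents it.**

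- Sections 9.1 and 9.3 state the same single-record rule, so they do not prevent it.
- The missing category (sections 9.7.3 and 9.9) applies when no value exists. Here a value exists and is contradicted.
- The promise in section 9.9 to use all earlier data is confined to comorbidities.

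So no passage reconciles conflicting smoking entries.

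**3. How much it could matter.** The protocol gives no smoking prevalence and no frequency of conflicting entries, so there is no plan figure to reproduce. What follows is illustration only.

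Assumptions: true ever-smoking e is 52% in the Spiriva group and 46% in a comparator; 60% of ever smokers are ex-smokers; a share x of ex-smokers has 'never' as the closest record. All records are taken as present, so the missing category is left out.

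Formulas:

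- Observed ever-smoking = e − x × 0.6 × e
- ASD = |p1 − p2| / √{[p1(1 − p1) + p2(1 − p2)] / 2}

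Without error: 0.06 / √[(0.52×0.48 + 0.46×0.54)/2] = 0.06 / 0.4990 = 12.0%.

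With x = 0.15 in the Spiriva group: 0.52 − 0.15×0.6×0.52 = 0.4732. With x = 0.05 in the comparator: 0.46 − 0.05×0.6×0.46 = 0.4462. The ASD is 0.0270 / 0.4982 = 5.4%.

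| x, Spiriva | x, comparator | Observed ever-smoking | ASD |
|---|---|---|---|
| 0 | 0 | 52.0% vs 46.0% | 12.0% |
| 5% | 5% | 50.4% vs 44.6% | 11.7% |
| 15% | 15% | 47.3% vs 41.9% | 11.0% |
| 15% | 5% | 47.3% vs 44.6% | 5.4% |
| 5% | 15% | 50.4% vs 41.9% | 17.3% |

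Upward crossing needs a true ASD below 10%. With true ever-smoking of 50% vs 46% (ASD 8.0%) and x of 5% vs 15%, the observed figures are 48.5% vs 41.9%, ASD 13.4%.

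**4. A second set of assumptions, on the ex-smoker share alone.** With 30% vs 25% true ex-smokers, the ASD is 11.2%. Equal x of 5%, 10% or 20% gives 10.8%, 10.4% or 9.7%. In the expected Spiriva group of 935 (section 9.5), that moves about 935 × 0.30 × x = 14, 28 or 56 patients to 'never'. Unequal x of 20% vs 10% gives 3.6%, and 5% vs 20% gives 19.9%.

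Equal error therefore shifts the ASD by up to about 1.5 points and crosses 10% only where the true value lies close to it. Larger movements need error that differs between the groups.

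**The case against.** The strongest reply is that the most recent record is a recognised choice, stated consistently in three places and applied alike to alcohol, BMI and blood pressure. The document does not contradict itself, and conflicting entries could be handled in a programming specification. The first part stands: this is a better rule, not an error in the text. The last part is weaker. The protocol states a rule rather than leaving it open, section 9.8 says the protocol will be strictly followed with changes made by amendment, and Annex 1 lists no stand-alone documents.

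The second reply is that nothing shows 'never' after a smoking entry to be common. Section 9.9 speaks of poor recording in general and answers only for missing values. This stands, and it is why no size can be claimed.

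The third concerns direction. A reader might infer that the error can only understate smoking. The documents do not support that: the older smoking entry may be the mistake and the later 'never' its correction. Understatement is a tendency, not a certainty.

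The fourth concerns the threshold. A reader might infer that the rule will hide a meaningful group difference. The fall to 5.4% rests on an assumed threefold difference in error. In that example the misclassified share of recorded never smokers is 4.68/52.68 = 8.9% in the Spiriva group, but only 1.38/55.38 = 2.5% in the comparator. Reversing the two error rates raises the ASD to 17.3%. More frequent reviews in one group might produce more conflicting entries, but might equally improve recording, and the protocol gives no review frequency by group.

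Finally, smoking is one of many descriptive covariates. It is neither an outcome nor an eligibility criterion, and no adjusted model uses it. That limits the severity.

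**Conclusion.** The point holds as a weakness in how one covariate is defined. As written, section 9.3.3 lets a closest 'never' entry override earlier smoking records that are already held, and neither the missing category nor the full-history promise for comorbidities covers this. The never/ex/current reading is inferred, because the categories are not listed.

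The size is unknown. If conflicting entries are equally frequent in the groups, the ASD changes little. If the frequency differs, the ASD could cross 10% in either direction. The documents do not show that it differs, so they support neither a claim that channeling by smoking would be missed nor a claim that it would be exaggerated. No outcome result is affected. Minor to moderate.

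**What to change.** In section 9.3.3, list the smoking categories and keep the closest record to separate current from ex-smokers. Add one rule: a patient whose closest record is 'never' and who has any earlier current- or ex-smoker record is classified as an ex-smoker. Report the number reclassified in each group, and show the closest-record tabulation and its ASD alongside as a check.

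The cost is a sentence or two in the protocol and a few lines of code on data already held. The downside is that an erroneous old smoking entry would turn a true never smoker into an ex-smoker. The counts per group and the side-by-side result let the reader judge how much the choice matters.

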8. RESEARCH QUESTION AND OBJECTIVES

The primary objective of the study is to describe the clinical and socio-demographic characteristics of asthma patients at the time of the initial prescription of Spiriva Respimat for the treatment of Asthma within a general clinical population using the GOLD database within Clinical Practice Research Datalink (CPRD).

A secondary objective will be to describe and compare the characteristics of asthma patients who initiated Spiriva Respimat to asthma patients who initiated a higher dose of ICS/LABA FDC, or LTRA, or alternatively those who switched to a new ICS/LABA FDC.

Protocol for non-interventional studies based on existing data

BI Study Number 0205-0537

[figure not shown]
c25002535-01

 Proprietary confidential information © 2018 Boehringer Ingelheim International GmbH or one or more of its affiliated companies

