9.3.2 Outcomes

9.3.2.1 Primary outcomes

The primary outcome is whether patient has Cardiac arrhythmias on the index date or in the year prior to the index date. Cardiac arrhythmias is defined as having the following readcode in the above mentioned time period:

medcode	readcode	readterm
17597	327..00	ECG: supraventricular arrhythmia
19707	328..00	ECG: ventricular arrhythmia
29371	328Z.00	ECG: ventricular arrhythmia NOS
97780	G559.00	Arrhythmogenic right ventricular cardiomyopathy
6503	G57..11	Cardiac arrhythmias
426	G577.00	Sinus arrhythmia
31690	G57yA00	Re-entry ventricular arrhythmia
53893	Gyu5a00	[X]Other specified cardiac arrhythmias
26670	2432.00	O/E - pulse irregularly irreg.
18746	662S.00	Atrial fibrillation monitoring
45773	6A9..00	Atrial fibrillation annual review

Protocol for non-interventional studies based on existing data

BI Study Number 0205-0537

c25002535-01

Proprietary confidential information © 2018 Boehringer Ingelheim International GmbH or one or more of its affiliated companies

9479	7936A00	Implant intravenous pacemaker for atrial fibrillation
92361	793M000	Perc translum ablat pulmon vein to lft atrium conduct system
105554	8CMW200	Atrial fibrillation care pathway
57832	9Os..00	Atrial fibrillation monitoring administration
90187	9Os0.00	Atrial fibrillation monitoring first letter
90188	9Os1.00	Atrial fibrillation monitoring second letter
90189	9Os2.00	Atrial fibrillation monitoring third letter
90190	9Os3.00	Atrial fibrillation monitoring verbal invite
90191	9Os4.00	Atrial fibrillation monitoring telephone invite
63350	9hF..00	Exception reporting: atrial fibrillation quality indicators
39114	9hF1.00	Excepted from atrial fibrillation qual indic: Inform dissent
2212	G573.00	Atrial fibrillation and flutter
1664	G573000	Atrial fibrillation
35127	G573300	Non-rheumatic atrial fibrillation
96277	G573400	Permanent atrial fibrillation
96076	G573500	Persistent atrial fibrillation
23437	G573z00	Atrial fibrillation and flutter NOS

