9.3.2.2 Secondary outcomes

The secondary outcome is whether patient has Cardiac failure on the index date or in the year prior to the index date. Cardiac failure is defined as having the following readcode in the above mentioned time period:

medcode	readcode	readterm
15058	14A6.00	H/O: heart failure
46912	14AM.00	H/O: Heart failure in last year
21235	1J60.00	Suspected heart failure
9913	1O1..00	Heart failure confirmed
46672	388D.00	New York Heart Assoc classification heart failure symptoms
106198	661M500	Heart failure self-management plan agreed
83502	662p.00	Heart failure 6 month review
12366	662T.00	Congestive heart failure monitoring
30779	662W.00	Heart failure annual review
95835	679X.00	Heart failure education
60099	67D4.00	Heart failure information given to patient
46636	68B6.00	Heart failure screen
105542	8CeC.00	Preferred place of care for next exacerbation heart failure
32945	8CL3.00	Heart failure care plan discussed with patient
103732	8CMK.00	Has heart failure management plan
106008	8CMW800	Heart failure clinical pathway
32898	8H2S.00	Admit heart failure emergency
17851	8HBE.00	Heart failure follow-up
91288	8Hg8.00	Discharge from practice nurse heart failure clinic
102585	8HgD.00	Discharge from heart failure nurse service
26115	8HHb.00	Referral to heart failure nurse
70619	8HHz.00	Referral to heart failure exercise programme

Protocol for non-interventional studies based on existing data

BI Study Number 0205-0537

c25002535-01

Proprietary confidential information © 2018 Boehringer Ingelheim International GmbH or one or more of its affiliated companies

71235	8Hk0.00	Referred to heart failure education group
48897	8HTL.00	Referral to heart failure clinic
106894	8IE1.00	Referral to heart failure exercise programme declined
90935	9hH..00	Exception reporting: heart failure quality indicators
30749	9hH0.00	Excepted heart failure quality indicators: Patient unsuitabl
64062	9hH1.00	Excepted heart failure quality indicators: Informed dissent
106545	9m5..00	High risk of heart failure screening invitation
12627	9N0k.00	Seen in heart failure clinic
19002	9N2p.00	Seen by community heart failure nurse
95021	9N4s.00	Did not attend practice nurse heart failure clinic
83481	9N4w.00	Did not attend heart failure clinic
69062	9N6T.00	Referred by heart failure nurse specialist
32911	9Or..00	Heart failure monitoring administration
19380	9Or0.00	Heart failure review completed
90193	9Or1.00	Heart failure monitoring telephone invite

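### The exacerbation count and the oral corticosteroid row stop before the index date, so an attack first recorded on the day treatment changes appears in no row

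*Protocol*

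**What the plan says.** Protocol section 9.2 defines the index date as the date of the prescription that starts, increases or switches treatment. Section 9.3 makes that date the default source for every variable, falling back to the closest earlier record, unless otherwise specified.

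Section 9.3.3 then lists "Number of asthma exacerbations in the year prior to the index date". A qualifying event is a course of "oral corticosteroids (OCS) (not prescribed during an annual asthma review), or an Accident and Emergency (A&E) visit, or hospital admission". A merging rule follows: "Exacerbations recorded within 14 days after the index 1 were considered part of the same exacerbation". The word index in that rule is best read as the first record of the exacerbation, not the study index date. OCS use is also a row under "Asthma-related prescriptions in the year prior to index date".

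Both cardiac variables are worded differently: "The primary outcome is whether patient has Cardiac arrhythmias on the index date or in the year prior to the index date" (section 9.3.2.1) and "The secondary outcome is whether patient has Cardiac failure on the index date or in the year prior to the index date" (section 9.3.2.2).

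**The concern.** Step-up treatment may be prescribed at the visit where an attack is treated. If the OCS course and the new controller are issued together, both carry the index date. A patient with no earlier event in the year is then tabulated with no exacerbation and no OCS use.

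This covariate matters more than most. The UK indication quoted in section 7 requires one or more severe exacerbations in the previous year, so exacerbation history bears directly on who is prescribed Spiriva. Section 8 sets out to describe "asthma patients at the time of the initial prescription of Spiriva Respimat". The study exists to detect channelling, section 9.7.1 treats an ASD of at least 10% as meaningful, and section 7 says the results may guide the choice of propensity-score variables in later studies.

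**Working it through.** **1. Windows side by side (Protocol)**

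| Item | Section | Index date named as included? |
|---|---|---|
| Default for all variables | 9.3 | Yes |
| Other LAMA and COPD exclusions | 9.2 | Yes |
| Cardiac arrhythmias | 9.3.2.1 | Yes |
| Cardiac failure | 9.3.2.2 | Yes |
| RCP 3 Questions score | 9.3.3 | Yes |
| Eosinophil count | 9.3.3 | Yes |
| Exacerbation count | 9.3.3 | No |
| Hospitalisation counts | 9.3.3 | No |
| Asthma prescriptions, including OCS | 9.3.3 | No |

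No sentence says outright that the index date is excluded. It is the plain reading, because the authors name that date wherever they want it. No reason for the difference is given.

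**2. What is lost**

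- First qualifying record on the index date, nothing earlier in the year: count 0, OCS row negative. No other row recovers the event.
- First record on the index date, with a separate episode more than 14 days earlier: the patient still shows an exacerbation, but the count is one short.
- OCS course, A&E visit or admission recorded in the 14 days before: already counted, and the index-date record merges into it. Nothing is lost.
- OCS prescribed at an annual asthma review: not an exacerbation under either window.

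**3. Possible size (assumed proportions; the plan has no figure to reproduce)**

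For the proportion with at least one exacerbation, ASD = |p1 − p2| / √{[p1(1 − p1) + p2(1 − p2)] / 2}.

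*Scenario A.* Assume 60% of Spiriva starters and 50% of dose increasers have a pre-index exacerbation. Let x be the share of the remaining patients with a first one on the index date, so p becomes p + (1 − p)x.

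| x, Spiriva / dose increase | Proportions | ASD |
|---|---|---|
| index date not counted | 0.600 / 0.500 | 0.100/0.495 = 0.202 |
| 5% / 5% | 0.620 / 0.525 | 0.095/0.492 = 0.193 |
| 5% / 15% | 0.620 / 0.575 | 0.045/0.490 = 0.092 |
| 5% / 25% | 0.620 / 0.625 | 0.005/0.485 = 0.010 |

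In the Spiriva group, x = 5% moves the proportion from 60% to 62%. On the feasibility count of 935 (section 9.5) that is 0.02 × 935 ≈ 19 patients.

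*Scenario B.* Assume equal pre-index proportions (ASD 0). Add the share of all patients in each group whose only exacerbation is first recorded on the index date.

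| Pre-index p | Added, Spiriva / comparator | ASD |
|---|---|---|
| 0.30 | 5% / 5% | 0.000 |
| 0.30 | 5% / 0% | 0.107 |
| 0.30 | 10% / 5% | 0.103 |
| 0.50 | 5% / 5% | 0.000 |
| 0.50 | 5% / 0% | 0.100 |
| 0.50 | 10% / 5% | 0.101 |

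With nothing added in the comparator, the smallest gap that reaches 0.10 is about 4.7 points at p = 0.30 (0.047 × 935 ≈ 44 Spiriva patients) and 5.0 points at p = 0.50 (0.050 × 935 ≈ 47).

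The planned variable is a number of exacerbations. For a mean count, the ASD moves by roughly the between-group gap in added episodes per patient, divided by the pooled SD. The documents give no SD, so this cannot be evaluated.

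**The case against.** A year-prior count is an ordinary baseline choice. Section 9.3 allows exceptions to its default, and section 9.3.3 makes one, so a reader who infers that the protocol contradicts itself goes too far. The abstract and section 9.7.1 describe characteristics before initiation, which fits a pre-index window as well as section 8 fits one that includes the day. The cardiac outcomes record presence, and the RCP score and eosinophil count take the closest value; exacerbations are events counted over a fixed year. All of this stands. What remains is that the difference is unexplained and falls on the day most likely to hold the triggering event.

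Including the day has its own error. Records carry dates, not times: a same-day A&E visit or admission may follow the prescription, and a same-day OCS course need not treat an attack. That also stands, and is the reason for a separate row. The RCP score does use the index date and reflects symptom control at the visit, but it does not register an attack or an OCS course.

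A reader might want the whole asthma-prescription list and the hospitalisation counts moved too. The documents do not support that. The list contains LTRA, so including the index date would mark every LTRA initiator as a prior user. For hospitalisations nothing in the protocol suggests a comparable loss.

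The day-0 boundary could be left to a SAP, but here the protocol itself has already worded the window.

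**Conclusion.** The point holds as a worthwhile correction to one definition. As worded, an exacerbation first recorded on the index date appears in no row, and exacerbation history at initiation is understated by however many such patients there are.

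A reader might infer from the scenarios that the Spiriva comparison is biased, or that the ASDs with index-date events added are the true ones. Neither follows. All the proportions are assumed, and they describe a yes/no version of a variable planned as a count. Scenario A puts the excess among dose increasers and scenario B among Spiriva starters, and nothing in the documents favours either. With equal loss the ASD hardly changes. The supportable statement is that a between-group gap of about 5 percentage points, if it exists, would be enough to move a proportion-based ASD across the 10% cut-off.

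**What to change.** In section 9.3.3:

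- Give the exacerbation count and the OCS row the same window as the cardiac outcomes in section 9.3.2, that is, the index date plus the year before it.
- Keep the annual-review exclusion and the 14-day merging rule, so that an index-date record continuing an attack already counted is not counted twice. Reword the merging rule so that its index plainly means the first record of the episode.
- Add one row for exacerbations first recorded on the index date. Both versions of the count are then visible, as is the part that may not be a true pre-treatment attack.
- Leave the other asthma-prescription rows, notably LTRA, and the hospitalisation counts as year-prior.

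The cost is a few words in the protocol, one date boundary in the program and one table row, with no new data. The downside is that some same-day OCS records will not be attacks or will not precede the index prescription; the separate row shows how many patients this could concern.
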